Recently, our study team completed a prospective, pilot single-arm trial of 20 participants with persistent COVID-19-associated OD who underwent bilateral stellate ganglion blocks and were followed for 1 month post-procedure. At 1-month, 10 (50%) participants experienced at least slight subjective improvement in their OD, 11 (55%) attained a clinically meaningful improvement in smell identification using the UPSIT, and 7 (35%) achieved a clinically meaningful improvement in olfactory-specific QOL. Therefore, we propose a double-blinded, placebo-controlled randomized clinical trial assessing the efficacy of a stellate ganglion block versus saline injection in a total of 140 participants with persistent COVID-19-associated parosmia.

C Study Objectives

C1 Primary Aim

1. To determine the efficacy of a SGB in improving parosmia-related quality of life compared to saline injection

C2 Secondary Aim

1. To determine the efficacy of a SGB in improving self-reported parosmia compared to saline injection
2. To determine the safety and tolerability of a SGB
3. To determine if subjects who catastrophize their parosmia smell loss are more likely to respond to SGB
4. To determine if subjects who screen positive for anxiety/depression are more likely to respond to SGB
5. Explore if there is variation of SGB effect dependent on injection laterality (right versus left SGB)

C3 Rationale for the Selection of Outcome Measures

Parosmia Olfactory Dysfunction Outcomes Rating (DisODOR). The DisODOR is a disease-specific questionnaire that assesses for physical problems, functional limitations, and emotional consequences of parosmia secondary to any etiology. The instrument contains 29 total items with each scored on a 5-point Likert scale from 0 to 4.

Clinical Global Impression - Severity Scale (CGI-S). The baseline severity of parosmia will be measured with the *CGI-S* scale. The *CGI-S* scale measures disease severity in clinical condition based on a 5-point Likert scale.

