Clinical Global Impression - Improvement Scale (CGI-I). The overall response to treatment will be measured with the *CGI-I* scale. The *CGI-I* Scale measures response to treatment for a number of disorders and has good internal consistency and validity.³² The *CGI-I* scale measures change in clinical condition based on a 7-point Likert scale. The *CGI-I* for parosmia asks, “Compared to before your stellate ganglion block, how would you describe your parosmia (things do not smell the same as you remember)?” Response options for each are: (1) Much better now than before, (2) Moderately better now than before, (3) Slightly better now than before, (4) About the same, (5) Slightly worse now than before, (6) Moderately worse now than before, and (7) Much worse now than before. Responders are defined as those who report “slightly better now than before” or greater.

University of Pennsylvania Smell Identification Test (UPSTIT, Sensonics, New Jersey). The *UPSTIT* is a test of olfactory identification and consists of four 10-page booklets, with a total of 40 items. On each page, there is a different “scratch and sniff” strip and four choice options. Subjects are asked to scratch each strip with a pencil to release the scents, detect the smell, and identify the smell from the four choice options. The *UPSTIT* comes from a scoring rubric that identifies the normalcy benchmark based on age and gender, which is >34 in women and >33 in men.^{33,34} The *UPSTIT* is commercially available, takes 10-15 minutes to complete, and is the gold standard test to assess smell identification. The minimal clinically important difference of the *UPSTIT* is 4.

Long-COVID Questionnaire (LCQ). Symptoms assessed via the *LCQ* are derived from the Symptom Burden Questionnaire for Long Covid³⁵, which included tiredness/fatigue, shortness of breath, brain fogginess, headache, cough, depression, low-grade fevers, palpitations, dizziness, muscle pain, and joint pains. At baseline, participants are asked to rank the current severity of each problem on a 5-point Likert scale. At each follow-up visit, participants are asked to rank their overall improvement in each of the 11 symptoms compared to their symptoms prior to their first SGB. The improvement options are based on the *CGI-I* 7-point Likert scale.

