Olfaction Catastrophizing Scale (OCS). The pain catastrophizing scale (PCS) was developed to measure the negative mental response to actual or anticipated pain. The *OCS* was derived from the validated PCS to similarly measure the negative mental response to smell dysfunctionloss. Multiple thoughts/feelings will be assessed on a 5-point likert scale with a maximum score of 52. At each visit, subjects will be asked to complete the *OCS*.

Hospital Anxiety and Depression Scale (HADS). The *HADS* was developed for screen for anxiety and depression in the general population. It consists of 7 questions for anxiety and 7 questions for depression each ranked on a 4-point Likert Scale. A score of 0-7 is considered normal, 8-10 is borderline abnormal anxiety or depression, and a score of 11-21 corresponds with screening positive for anxiety or depression. Subjects will be screened for anxiety and depression at eachtheir initial visit.

Pre-Intervention Expectations. A significant number of social media and news stories have discussed anecdotal success of stellate ganglion blocks for COVID-19-induced olfactory dysfunction. As a result, we propose that participants may have a distorted pre-operative expectation that may affect their subjective rating of improvement in olfaction. Therefore, participants will be asked at baseline, "How confident are you that the stellate ganglion block will improve your smell loss or smell distortion?" Possible answer choices: Not at all, Slightly confident, Somewhat confident, Very confident, Extremely confident.

Patient Satisfaction with Treatment. Participants will be asked at the 1-month virtual visit, "Overall, how satisfied were you with the stellate ganglion block treatment for your parosmia?" Possible answer choices: 1) Completely dissatisfied, 2) Mostly dissatisfied, 3) Somewhat dissatisfied, 4) Neither satisfied or dissatisfied, 5) Somewhat satisfied, 6) Mostly satisfied, 7) Completely satisfied. Patients will also be asked at the final visit, "Would you recommend this treatment to a family member or close friend who also suffers from chronic smell loss due to COVID-19?" Possible answer choices: 1) Yes, 2) No.

Assessment of the Blind. Immediately after the initial injection, participants will be asked, "Which intervention do you think you received?" Answer choices: 1) Mepivacaine (active medication) 2) Saline (placebo).

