Placebo Injection. The placebo sham injection will be performed in an identical fashion as the stellate ganglion block by [name] with the exception of using 6-8 mL of 0.9% saline injection instead of mepivacaine. A Horner syndrome is not expected after placebo injection, but its presence has been noted in prior studies with sham SGBs.

F Study Procedures

F1 Screening for Eligibility

To determine potential eligibility for the study, the research team will query the medical record and our team's contact database of COVID-19-induced olfactory dysfunction patients based on the inclusion/exclusion criteria. For those meeting the selection criteria, we will access name, telephone number, age, sex, and date/time of any upcoming clinic visits. For interested and potentially eligible individuals, including those contacting the study team, eligibility will be determined based on the inclusion/exclusion criteria and completion of the DisODOR questionnaire. If they have been treated at the medical center for COVID, their medical record will be accessed.

F2 Schedule of Measurements

The first visit will be completed at the Clinical and Translational Research Unit (CTRU). The second and third visits will be completed virtually.

Role of the CTRU: Nursing staff will be needed for assistance in completion of the SGB. Additionally, all subjects will have vital signs monitored with serial blood pressures, respiratory rate, heart rate, and pulse oximetry within the CTRU for a minimum of 10 minutes after completion of the block to ensure patient stability prior to discharge. Additional monitoring will be provided as needed based on patient response to the procedure. Participants will be discharged once stability is determined and instructed to continue wearing an eye patch for an additional 2 hours. It will be ensured that they have someone to drive them home prior to discharge.

Visit 1

At the initial visit, demographic information, including age, sex, race, and length of time of parosmia will be collected from each enrolled patient. Prior to undergoing the first SGB, participants will complete the Parosmia trigger question, DisODOR, UPSIT, CGI-S for Parosmia, OCS, HADS, and Pre-Intervention Expectations Questionnaire. The assessment of the blind will occur just prior to discharge from the first visit.

Visit 2

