We plan to perform an interim futility analysis. The recruitment will be halted and we will perform interim analysis when the first 40 subjects randomized and who have successfully completed treatment will have completed their 1-month post treatment assessment. Comparison of the primary endpoint between the 2 study groups will be evaluated for the interim futility analysis. Fisher's exact test will be used for the analysis given the small sample size. Conditional power (CP) with is the probability of finding statically significant results at the end of the trial, given the information obtained at interim analysis will be calculated using Mehta & Pocock CP equation. If CP<20% the result will be considered as suggestive of futility and it will serve only as a guideline that initiates more comprehensive discussion as to whether the course of the study should be modified. The data will be frozen for analysis and will be saved, so that additional analyses may be performed, or the analyses recreated, if necessary. Interim comparative data will be considered confidential and the results will be provided in a blinded fashion to research team members.

G3 Analysis Plan

Standard descriptive statistics will be used to describe distribution of baseline characteristics in each of the study groups. The effect of the intervention will be measured as the between-subject change in DisODOR.

The 95% confidence interval around this effect size will be determined to assess the precision of the observed effect and whether a clinically meaningful difference is plausible given the observed results. The DisODOR has an MCID of 15 points. A difference of at least 25% from the saline group is considered clinically meaningful. **If a greater than 25% proportion difference in responder rate is achieved in favor of the SGB group, we will offer the SGB to the placebo group at the conclusion of the study.** This will be submitted as a modification to the study.

Appropriate analyses will be performed for the secondary outcome measures.

H Data Handling and Record Keeping

H1 Confidentiality and Security

The secure REDCap database will be used to store data. Only study team members will have access to the database.

I Study Monitoring, Auditing, and Inspecting

I1 Study Monitoring Plan

The regulatory coordinator with the assistance of the study team will:

- Review of credentials, training records, and delegation of responsibility logs.
- Review of Consent Forms:

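### Baseline expectation is collected because it may affect self-rated improvement, but the analysis plan gives it no role: a modest, avoidable loss of precision, not a bias

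*Combined protocol and SAP*

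**What the plan says.** Under Pre-Intervention Expectations, section C3 refers to media reports of success with the block and states that "participants may have a distorted pre-operative expectation that may affect their subjective rating of improvement in olfaction". For that reason it asks, at baseline, "How confident are you that the stellate ganglion block will improve your smell loss or smell distortion", with five ordered answers. Section F2 places the item at Visit 1 before the injection, in the set "OCS, HADS, and Pre-Intervention Expectations Questionnaire".

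Section G3 defines the effect without naming any covariate: "The effect of the intervention will be measured as the between-subject change in DisODOR". Its only general statement on baseline data is "Standard descriptive statistics will be used to describe distribution of baseline characteristics in each of the study groups". For everything else it says "Appropriate analyses will be performed for the secondary outcome measures".

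The secondary aims in C2 name three possible modifiers of response: catastrophizing ("To determine if subjects who catastrophize their parosmia smell loss are more likely to respond to SGB"), anxiety or depression, and side of injection. Expectation is not among them. The randomisation section (2.d) describes permuted blocks at 2:1 and names no stratification factor.

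**The concern.** The protocol identifies a factor that may influence how participants rate themselves and measures it in everyone at the right time. It then assigns it no adjusted, stratified, subgroup or interaction analysis.

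This matters more here than in many trials because the follow-up has no objective efficacy measure. The schedule of events has the smell identification test at baseline only. DisODOR and CGI-I are both self-reported, and C3 says of the latter "The overall response to treatment will be measured with the *CGI-I* scale".

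Two consequences follow if expectation predicts the rating. Its contribution stays in the residual variance, so the interval is wider than it need be. In any one trial, a chance difference in expectation between arms also carries into the estimate. These are two views of the same variance component and should not be added together.

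**Working it through.** **Inputs.** From G1: 76 active and 38 control evaluable, 35% responders in the pilot, a target difference of 25 points, two-sided alpha 0.05, 80% power. The control rate of 10% is implied (35% − 25%), not stated. The correlation r between expectation and outcome is not in the documents and is varied below.

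**The plan's own figure.** Exact power of Fisher's test at 10% vs 35%, 38 vs 76, with 0.025 in each tail, is 81.2%. The smallest 2:1 total reaching 80% is 111, so the stated 114 is reproduced to within 3%. That figure is for a responder comparison, which matters in step 4.

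**1. Chance imbalance.** The standard error of a standardised baseline difference is sqrt(1/76 + 1/38) = 0.199, with a 95% range of ±1.96 × 0.199 = ±0.39 SD.
- P(|d| > 0.2): z = 0.2/0.199 = 1.01, so 31% of trials.
- P(|d| > 0.3): z = 0.3/0.199 = 1.51, so 13% of trials.

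**2. What an imbalance does to the estimate.**
- Continuous outcome: shift = r × d. With r = 0.3 and d = 0.3 it is 0.09 SD, or 0.09/0.199 = 0.45 of a standard error.
- Responder scale: assume half the participants have high expectation. The arm difference in that share has SD 0.5 × 0.199 = 0.099, so a 95% range of ±19.5 points. If high- and low-expectation participants differ in response by 10, 20 or 30 points, the shift has a 95% range of about ±1.9, ±3.9 or ±5.8 points, against a target of 25.

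**3. Precision, continuous DisODOR change.** Variance reduction = r²; standard error factor = sqrt(1 − r²); equivalent sample size = 114/(1 − r²).

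| r | Variance cut | SE factor | Equivalent N |
|---|---|---|---|
| 0.2 | 4% | 0.980 | 118.8 |
| 0.3 | 9% | 0.954 | 125.3 |
| 0.4 | 16% | 0.917 | 135.7 |

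In 4,000 simulated trials per setting, with an effect of 0.56 SD (unadjusted power about 80%), adjustment gave power of about 81%, 84% and 90% at r = 0.2, 0.3 and 0.5. With no effect, rejection rates were 4.5% to 5.4% with or without adjustment, and the mean estimate was essentially zero both ways.

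**4. Precision, responder difference.** The r² rule does not carry over to a binary endpoint. Simulating 76 vs 38 at 35% vs 10%, with r on the underlying continuous scale, the variance of the adjusted risk difference fell by about 0–2%, 2–3% and 3–5% at r = 0.2, 0.3 and 0.4. The ranges span repeated simulations. At r = 0 variance rose by about 1%.

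**The case against.** The strongest reply is that the design already deals with the main threat. Expectation is recorded before a randomised, blinded injection, so it is balanced on average, and the 95% confidence interval promised in G3 already allows for chance imbalance. This stands. A reader might infer from C3 that the unadjusted comparison is biased or its test invalid; the documents do not support that, and the simulation shows no inflation of error. Nor would adjustment repair any loss of blinding.

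A second temptation is to say the plan expects expectation to drive the outcome. C3 says only that it may affect ratings, and no strength of association is given.

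Third, the sample-size equivalents in step 3 (about 5, 11 or 22 participants on 114) should not be read against the trial's power statement. The 114 was derived for responder proportions, where the gain is much smaller. G3's wording permits a continuous analysis of DisODOR change but does not settle it.

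Fourth, adding a covariate to a logistic model would yield a conditional odds ratio, not the responder-rate difference on which the sample size and the 25% post-trial criterion rest. That is correct and shapes the fix.

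Two defences are weaker. A descriptive baseline table might reveal an imbalance, but nothing says what would be done about it, and adjusting after seeing it would be a data-driven choice. The sentence on secondary outcomes names no model or covariate and does not reach the primary outcome.

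**Conclusion.** The point holds as one of precision and uncorrected chance imbalance. The protocol gives its own reason for measuring expectation, and the analysis plan does not follow it through.

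The size is modest. For continuous DisODOR change, the gain is worth having if r is about 0.3 or more (a variance cut of 9% or more). For responder differences it is about 5% at most over the range of r examined. The chance shift of roughly 2 to 6 points is small against 25, though it could matter for a result close to the 25% line that G3 uses.

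All of this rests on assumed correlations and on the implied 10% control rate. If baseline DisODOR is also in the model, the relevant r is what expectation adds beyond it, which the documents do not allow one to estimate. The planned unadjusted result would remain valid; prespecifying the adjustment is a worthwhile improvement.

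**What to change.** In G3:

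- For DisODOR change, prespecify a linear model comparing arms, with the five-level expectation score as a linear term and baseline DisODOR as covariates.
- For the DisODOR and CGI-I responder endpoints, prespecify a covariate-standardised risk difference with its 95% confidence interval: fit the adjusted model, average the predicted response over all participants under each assignment, and take the difference. The 25-point target then keeps its meaning.
- Report the unadjusted comparison alongside each, and tabulate expectation by arm.

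No new data are needed. The expectation term costs one degree of freedom, and about 1% in variance if it turns out unrelated to outcome. The drafting is somewhat more than one sentence, because G3 does not yet specify a between-arm model to which a covariate could be added.

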Chronic olfactory dysfunction, both hyposmia and parosmia, from the COVID-19 pandemic is a growing public health crisis with up to 1.2 million people in the United States affected. Olfactory dysfunction impacts one's quality of life significantly by decreasing the enjoyment of foods, creating environmental safety concerns, and affecting one's ability to perform certain jobs. Olfactory loss is also an independent predictor of anxiety, depression, and even mortality. Recent research by our group (unpublished data) suggests that parosmias, moreso than hyposmias, can result in increased rates of anxiety, depression, and even suicidal ideation. While the pandemic has increased the interest by the scientific community in combating the burgeoning health crisis, few effective treatments currently exist for olfactory dysfunction. Persistent symptoms after an acute COVID-19 infection, or "Long COVID" symptoms, have been hypothesized to be a result of sympathetic positive feedback loops and dysautonomia. Stellate ganglion blocks have been proposed to treat this hyper-sympathetic activation by blocking the sympathetic neuronal firing and resetting the balance of the autonomic nervous system. Studies prior to the COVID-19 pandemic have supported a beneficial effect of stellate ganglion blocks on olfactory dysfunction, and recent news reports and a published case series have described a dramatic benefit in both olfactory function and other long COVID symptoms in patients receiving stellate ganglion blocks. A previous pilot study using stellate ganglion blocks of 20 participants with persistent COVID-19 olfactory dysfunction resulted modest improvements in subjective olfactory function, smell identification, and olfactory-specific quality-of-life, but it lacked a control group. Therefore, we propose a double-blinded, placebo-controlled randomized clinical trial assessing the efficacy of a stellate ganglion block versus saline injection in a total of up to 140 participants with persistent COVID-19-associated olfactory dysfunction.

A2 Primary Hypothesis

Stellate ganglion block (SGB) is effective and safe in improving olfactory dysfunction in patients with chronic COVID-19-induced parosmia.

A3 Purpose of the Study Protocol

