The purpose of this study is to evaluate the efficacy of stellate ganglion blocks for the treatment of chronic COVID-19-associated parosmia in order to treat the growing population of people with long-term olfactory dysfunction as a result of the pandemic.

B Background and Rationale

One of the hallmark symptoms of infection with SARS-CoV-2 is olfactory dysfunction (OD). While the majority of patients recover from COVID dysosmia, up to 15%-25% have long-term hyposmia^{1,2} and it is estimated that up to 1.2 million people in the United States will experience chronic OD from the COVID-19 pandemic.³ A unique feature of COVID-19-associated OD is the high rate of persistent parosmia. In one study of 222 patients with COVID-19-associated olfactory dysfunction by Lerner et al, 148 (67%) of these patients experienced parosmia at some point, and estimates of persistent parosmia 6 months after COVID-19 infection range from 25% to 57%.⁴⁻⁶ Patients with OD have decreased quality-of-life and have described their lives as if “living in a box.”⁷ These patients have concerns for environmental safety, decreased enjoyment of their food, depression, anxiety, and even a higher risk of mortality.⁷⁻⁹ Unpublished work by our group has demonstrated a relationship between parosmia and increased risk of screening positive for anxiety, depression, and suicidality.

The COVID-19 pandemic has highlighted the importance of the sense of olfaction, but no standard of care treatment for post-viral OD exists. The most commonly used treatment for post-viral OD is olfactory training; however, a large proportion of patients do not receive benefit and continue to have persistent symptoms.¹⁰ A multitude of other therapies have been tried in randomized clinical trials with minimal success, including theophylline¹¹, vitamin A¹², sodium citrate¹³, and intranasal insulin.^{14,15} As a result, there is a critical need for the development of a novel intervention to address the large number of patients with OD due to the COVID-19 pandemic.

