The study will be a single center, double-blinded, placebo-controlled randomized clinical trial conducted at Washington University School of Medicine.

E2 Subject Selection

2.a Inclusion Criteria

- 1) Adults age 18 to 70
- 2) Diagnosis of COVID at least 6 months prior to study enrollment with self-reported parosmia
- 3) Ability to read, write, and understand English
- 4) Score of at least 40 on DiSODOR during screening and at least 25 during Visit 1

2.a Exclusion Criteria

- 1) History of smell loss or change prior to COVID-19 infection
- 2) History of conditions known to impact olfactory function:
 - a. Chronic rhinosinusitis
 - i. If individual notes a history of chronic rhinosinusitis or prior endoscopic sinus surgery, they may be eligible if they can a note from their otolaryngology (ENT) physician stating the following:
 1. Patient's chronic rhinosinusitis is controlled
 2. There are no polyps/masses/scarring of the olfactory cleft
 3. The otolaryngologist feels that the patient's parosmia is secondary to COVID-19
 - b. History of prior sinonasal or skull base surgery
 - c. Neurodegenerative disorders (Parkinson's disease, Huntington's disease, Amyotrophic lateral sclerosis, Lewy body dementia, frontotemporal dementia)
- 3) Currently using concomitant therapies specifically for the treatment of olfactory dysfunction
- 4) Inability to tolerate a needle injection into the neck
- 5) History of coexisting conditions that make SGB contraindicated:
 - a. Unilateral vocal cord paralysis
 - b. Severe COPD (FEV1 between 30-50% of predicted)
 - c. Recent myocardial infarction within the last year

- d. Glaucoma
- e. Cardiac conduction block of any degree
- 6) Currently taking blood thinners or antiplatelet agents, including
> 81mg aspirin
- 7) Allergy to local anesthetic
- 8) Inability to extend the neck for any reason (e.g., severe arthritis)
- 9) History of prior stellate ganglion block

2.b Ethical Considerations

Patients will be informed in the informed consent process that they may or may not personally benefit from the study and that the data obtained from the study will be used to inform the future care patients with chronic COVID-19-induced olfactory dysfunction. There will be phone assistance available 24/7 during the study period to report any possible adverse reactions. There are no financial conflicts of interest.

2.c Subject Recruitment Plans and Consent Process

Study recruitment strategies include:

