The second visit will be virtual and will occur approximately 1 month after the first visit. Participants must have access to email and the internet to receive a link which will

connect them with the questionnaires to complete about their smell ability and how they are feeling. Their answers will be saved in REDCap. Participants will be asked to fill out the Parosmia trigger question and the DisODOR. They will also complete the CGI-I for Olfactory Dysfunction, the LCQ, the Participants Satisfaction with Treatment Questionnaire, OCS, HADS, and Adverse Events Assessment.

Visit 3

The third and final visit will be virtual and will occur approximately 3 months after the injection. Participants must have access to email and the internet to receive a link which will connect them with the questionnaires to complete about their smell ability and how they are feeling. Their answers will be saved in REDCap. At 3-months post-SGB, participants will virtually complete the Parosmia trigger question, DisODOR, CGI-I for Olfactory Dysfunction, LCQ, Participant Satisfaction with Treatment Questionnaire, OCS, HADS, and Adverse Events Questionnaire.

Schedule of Events	Visit 1		Visit 2 1 Month post SGB (=+/- 7 days)	Visit 3 3 Months post SGB (+/- 7 days)
	Screening*	Baseline		
Informed Consent	X			
Demographics Questionnaire**	X			
Inclusion/Exclusion Criteria	X			
Parosmia trigger question		X	X	X
CGI-S for Parosmia		X		
University of Pennsylvania Smell Identification Test (UPSIT)		X		
Pre-Intervention Expectations Questionnaire		X		
Parosmia Olfactory Dysfunction Outcomes Rating (DisODOR)	X	X	X	X
Olfaction Catastrophizing Scale (OCS)		X	X	X
Hospital Anxiety and Depression Scale (HADS)		X	X	X
Long-COVID Questionnaire		X	X	X
SGB or Placebo Injection		X		

Assessment of the Blind		X		
CGI-I for Parosmia			X	X
Participant Satisfaction with Treatment Questionnaire			X	X
Adverse Events Assessment		X	X	X

*Screening and Visit 1 may occur at the same visit

**Demographic variables include date of birth, sex, race, ethnicity, home address, date of (+) COVID-19 test

***The assessment of the blind will occur just prior to discharge from the first visit.

F3 Safety and Adverse Events

3.a Safety and Compliance Monitoring

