 - 100% reviewed for studies with < 100 subjects.
- Review reports on missed events, missing data, and protocol deviations for a determined sample of subjects.
- Compare source documentation and CRFs (REDCap database) to ensure data are accurate and complete.
- Regulatory review of IRB approvals in the Investigator Site File.

Monitoring Schedule:

- The first monitoring activities will occur within 1 month after first subject is enrolled.
- Interim monitoring activities will occur after 20 participants are enrolled and again when enrollment is met and all visits for all participants are completed.
- Ad hoc or for-cause monitoring as needed or requested.

J Attachments

J1 Questionnaires or surveys

- Assessment of the Blind
- Parosmia trigger question
- Parosmia Olfactory Dysfunction Outcomes Rating (DisODOR)
- CGI-S for Parosmia
- CGI-I for Parosmia
- Long-COVID Questionnaire
- Olfactory Catastrophizing Scale (OCS)
- Hospital Anxiety and Depression Scale (HADS)
- Pre-Intervention Expectations Questionnaire
- Participants Satisfaction with Treatment Questionnaire
- University of Pennsylvania Smell Identification Test (UPSIT)

K References

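### Inclusion criterion 2 times the COVID diagnosis but not the parosmia, so recent-onset parosmia can enter a trial whose hypothesis and purpose concern chronic parosmia

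*Combined protocol and SAP*

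**What the plan says.** The hypothesis in A2 is that "Stellate ganglion block (SGB) is effective and safe in improving olfactory dysfunction in patients with chronic COVID-19-induced parosmia". A3 gives the purpose as to "evaluate the efficacy of stellate ganglion blocks for the treatment of chronic COVID-19-associated parosmia".

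Eligibility is set in E2, 2.a. Item 2 reads "Diagnosis of COVID at least 6 months prior to study enrollment with self-reported parosmia". Item 4 is a severity rule: "Score of at least 40 on DiSODOR during screening and at least 25 during Visit 1". The footnote to the Schedule of Events adds that "Screening and Visit 1 may occur at the same visit".

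F2, Visit 1, says that "demographic information, including age, sex, race, and length of time of parosmia will be collected from each enrolled patient". The Schedule of Events footnote that lists the demographic variables includes the date of the positive COVID test but neither onset nor duration of parosmia. Duration is not mentioned in the randomization text (2.d) or in the analysis plan (G3).

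**The concern.** A trial of chronic parosmia needs a rule that makes the parosmia chronic. Item 2 sets a date for the infection only. Read literally, it admits a person whose COVID was 6 months ago and whose parosmia began last month. It arguably also admits a person with an old first diagnosis whose parosmia followed a recent reinfection.

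Section B opens its epidemiology with "While the majority of patients recover from COVID dysosmia". If some recent-onset cases are still improving without treatment, they can gain the 15 DisODOR points that define a response whichever injection they receive. Such participants add responders to both arms and nothing to the difference between them. The result would then describe a mixture of recent and long-standing parosmia. The responder difference on which G1 bases the sample size, and which G2 and G3 also use, could be smaller than planned.

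**Working it through.** **1. Does anything else close the gap?**

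- Exclusion 1 removes smell change that preceded COVID-19. It is silent on parosmia that began recently after COVID-19.
- The DisODOR thresholds measure severity, not duration. Both scores may be taken on one day. If they are taken on different days, a fall from 40 to 25, which is 15 points or one full MCID, still qualifies.
- One recruitment route (2.c) targets chronic cases, but others do not, and recruitment text is not an eligibility criterion.
- Duration is collected but is used neither to select participants nor to analyse them.

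Nothing closes it.

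**2. Reproducing G1.** Inputs from G1: 35% pilot response (at least 15 points), a 25-point difference, 76 active and 38 control, exact test, two-sided 0.05, 80% power. The control rate is not stated; 35% − 25% = 10% is inferred. Exact power of Fisher's test at 10% vs 35%:

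- with 0.025 in each tail, power is 81.2% at 114 and the smallest 2:1 total reaching 80% is 111;
- with the usual minimum-likelihood two-sided p-value, power is 84.1% at 114 and the smallest total is 108.

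The plan's 114 is therefore consistent with 10% vs 35%. Taking 35% as the control rate (35% vs 60%) gives only 64.0% or 69.3%, so that reading does not fit.

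**3. Illustration of dilution.** Let f be the recent-onset share and s the spontaneous 1-month response in those cases. Both are assumed, because the documents give neither.

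- Control rate: c = 0.10(1 − f) + s·f.
- Active rate if the block adds nothing in recent-onset cases: a = 0.35(1 − f) + s·f, so the difference is 0.25(1 − f).
- Active rate if the block keeps its full effect in them: a = c + 0.25.

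Example with f = 10%, s = 70%, no added effect: c = 0.09 + 0.07 = 16%; a = 0.315 + 0.07 = 38.5%; difference 22.5 points; power 69.2%.

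Results for f = 10% at 76 vs 38 (minimum-likelihood version, baseline 84.1%):

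| s | Control | Active, no added effect | Power | Active, 25 points kept | Power |
|---|---|---|---|---|---|
| 10% | 10.0% | 32.5% | 76.1% | 35.0% | 84.1% |
| 35% | 12.5% | 35.0% | 72.7% | 37.5% | 81.3% |
| 50% | 14.0% | 36.5% | 71.1% | 39.0% | 79.8% |
| 70% | 16.0% | 38.5% | 69.2% | 41.0% | 78.1% |

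The version with 0.025 in each tail runs lower: from a baseline of 81.2%, the no-added-effect column becomes 72.8% to 64.1% over the same values of s.

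**The case against.** The strongest reply is that the trial is randomized with a concurrent saline arm, so natural recovery falls on both arms alike. That stands. A reader might infer that recent-onset cases bias the comparison; the design does not support that reading.

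A second reply is that the power loss cannot be measured from the documents. That also stands, for four reasons:

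- The 35% comes from an uncontrolled pilot and already contains whatever natural recovery occurred there. The inferred 10% may contain some as well. Adding further recovery assumes that this trial takes in more recent-onset cases than the planning rates reflect.
- If the block works as well in recent-onset cases, little power is lost.
- Section B's remark on recovery concerns COVID dysosmia in general, not parosmia present 6 months after infection. Its figures of 67% ever affected and 25-57% at 6 months come from different sources, so the gap between them is not a recovery rate.
- The one pointer to late onset is the title of reference 5, "Phantosmia, Parosmia, and Dysgeusia Are Prolonged and Late-Onset Symptoms of COVID-19", which gives no frequency.

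A third reply is that Section B itself times persistent parosmia from infection, so item 2 follows house usage. This stands only in part. Persistence in that passage means parosmia still present at 6 months, whereas item 2 does not ask that it has persisted. Item 2 may also be read as tying the diagnosis to the episode that caused the parosmia, which would rule out the reinfection example. Neither reading supplies a duration.

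**Conclusion.** The gap in the wording is real: as written, item 2 admits recent-onset parosmia, which lies outside the population named in A2 and A3. The certain consequence is uncertainty about whom the result describes. A smaller responder difference and lower power are possible, but their size is unknown.

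With a 10% recent-onset share, the illustration gives about 69-76% power if the block adds nothing in those cases and about 78-84% if it keeps its 25-point effect, against 84% at baseline. These ranges rest on an assumed share, an assumed spontaneous response of 10-70%, an inferred 10% control rate and one version of Fisher's test. A reader might take them as showing that the trial is underpowered; the documents do not support that. The change is still worth making, because it is cheap and the population should match the stated aim.

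**What to change.** Reword inclusion item 2 so that the existing 6-month minimum applies both to the COVID diagnosis and to the current parosmia attributed to COVID-19. There is no need to require that the parosmia was continuous. Ask the parosmia-duration question from Visit 1 at screening instead, and add onset or duration to the Schedule of Events list and to REDCap, so that the value is certain to be recorded.

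For participants already enrolled, or if eligibility cannot be changed, pre-specify two analyses before unblinding:

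- a supportive analysis of DisODOR change or response adjusted for parosmia duration, with the model named, since Fisher's test cannot adjust and G3 names no model;
- a sensitivity analysis limited to participants whose parosmia had lasted at least 6 months at enrollment. Duration is a baseline value, so arms within that subset remain comparable by randomization.

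The cost is a short amendment, one question moved and one field added. A few recent-onset candidates become ineligible or must wait.
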